### **Research Objectives**

Research Question: Among inpatients with positive urine cultures reported by Health Sciences microbiology laboratory, would restricted reporting, as compared to standard reporting, lead to a reduction in the rate of inappropriate antibiotic therapy without an increase in UTI or pyelonephritis (kidney infection)?

Primary efficacy outcome: proportion of inappropriate antibiotic therapy prescribed by physicians based on published diagnostic criteria for AB and UTI [2, 4, 17] in an intention to treat population. Inappropriate therapy is defined as any treatment for AB, or no treatment for UTI, or treatment for UTI to which the isolated bacteria is resistant.

Primary safety outcome: proportion of untreated UTI and untreated bacteremia.

Secondary efficacy outcomes: proportion of calls from physicians requesting complete report, drug cost savings based on reduction in treatment.

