### **Methodology**

The proposed study is a randomized trial of two methods of laboratory reporting in which physicians are the main research participants. At the time of positive urine culture results, the patient will be randomized by computer generated random number placed into serially numbered sealed, opaque envelopes in two equal groups. One group will receive restricted reporting, with a report that states "This POSITIVE urine culture may represent asymptomatic bacteriuria or urinary tract infection. If urinary tract infection is suspected clinically, please call the microbiology laboratory at [name] between 0900 to 2300, or the microbiology technologist on-call at [name] at night, for identification and susceptibility results." The other group will receive conventional reporting of identification and susceptibility. Physicians will then have the option of calling the laboratory to receive the results or not. Complete results will be released by telephone and Meditech to physicians who call to request them. Physicians will be informed about the study prior to initiation, and debriefed about the study after the results have been collected.

Inclusion criteria will include consecutive positive urine cultures collected from adults in acute care that are greater than or equal to 18 years of age. Inpatients must be admitted to Health Sciences Center or St. Clare's Mercy hospitals only, in order to facilitate access to inpatient records. Exclusion criteria will include pregnancy, antibiotic treatment at the time of collection, collection from an indwelling urinary catheter, patients in the Intensive Care Unit and patients with blood neutrophils  $<1.0$  within 7 days, which will help protect immunocompromised individuals. Furthermore, [name] will review patient charts at 24 and 72 hours and 7 days after collection to ensure patients experience minimal adverse events.

After randomization and reporting, a physician investigator will assess inpatients for the true diagnosis of AB or UTI. Health records will be accessed including demographics, treatment

decisions and outcomes (untreated UTI or pyelonephritis). Frequency of physician calls requesting complete reporting will be recorded.

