The microbiology laboratory at Health Sciences Center receives 130 urine specimens per day, with 30 percent reported as significant growth (40 specimens per day). Twenty-five percent are submitted from inpatients. Method of collection will be determined prior to randomization. Study data collection and analysis will take place at the microbiology laboratory only.

The research hypothesis is that restricted reporting will reduce the rate of inappropriate treatment prescribed by physicians. Among inpatients, the expected rate of inappropriate treatment in the control group will be 45 percent, and 15 percent in the intervention group. Accepting a risk of type 1 error of five percent, and a risk of type 2 error of twenty percent, the study will recruit 84 patients. In order to account for missing data, recruitment will be increased to 100 patients. This will require approximately ten days of recruitment. The statistical test to be used is a comparison of proportions between two groups (T test, two sided analysis). Because true diagnosis may be biased by lack of access to clinical information, an intention to treat analysis including all patients randomized will be performed.

Physicians must remain unaware of the research project so that their treatment decisions are unbiased. However, a general notice will be sent to all physicians regarding the study design, and a debrief will be provided in which study results are presented and the option to withdraw data will be provided. This will cause physicians to feel less deceived while still not informing them of the study and thus will not change their behavior.

Physicians of discharged inpatients will be contacted at 7 days to assess for adverse events. Because recruitment will be brief, it is unlikely that physicians will have a second patient in the study.

Ethics permission will be sought from the local ethics board. Consent of patients or physicians will not be requested. In compliance with TCPS requirements, participants will experience no more than minimal risk. [name] who will assess inpatient charts at 24 and 72 hours and 7 days to surveil adverse events. If an adverse event occurs, the patient will be removed from the study immediately and given standard treatment. Physician consent will not be requested, as awareness of the study would bias treatment decisions.

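### Removing a patient from the study after an undefined adverse event conflicts, read literally, with the intention-to-treat analysis, and leaves open how a UTI found untreated at a study review is counted

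*Combined protocol and SAP*

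**What the plan says.** All the relevant text is in the combined protocol and SAP.

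- **Removal rule (Methodology, ethics paragraph):** "If an adverse event occurs, the patient will be removed from the study immediately and given standard treatment".
- **Analysis set (Methodology, sample size paragraph):** "an intention to treat analysis including all patients randomized will be performed". Research Objectives also sets the primary efficacy outcome in an intention-to-treat population.
- **Safety outcome (Research Objectives):** "Primary safety outcome: proportion of untreated UTI and untreated bacteremia".
- **Efficacy outcome (Research Objectives):** "proportion of inappropriate antibiotic therapy prescribed by physicians", with the definition "Inappropriate therapy is defined as any treatment for AB, or no treatment for UTI". Treating a UTI with a drug to which the organism is resistant also counts as inappropriate.
- **Reviews (Methodology):** an investigator "will review patient charts at 24 and 72 hours and 7 days after collection to ensure patients experience minimal adverse events". For patients who have left hospital, "Physicians of discharged inpatients will be contacted at 7 days to assess for adverse events".

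The plan does not define adverse event. It does not say what happens to a removed patient's data or remaining reviews, and it sets no time at which a UTI is fixed as untreated.

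**The concern.** There are two gaps.

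The first holds whatever adverse event means. A patient removed from the study and a patient analysed as randomized are different things, and the plan promises both. Removal may also cut short observation for bacteremia and pyelonephritis, although even discharged patients are followed to day 7.

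The second depends on the meaning of the term. The patient risk that the Methodology section names is a UTI left untreated, and standard treatment is the natural answer to it. If that is the adverse event, the event that triggers removal is also the one the safety outcome must count, and it is part of the efficacy outcome too. The 24-hour and 72-hour reviews fall before day 7, so such a UTI could be treated because of the study before it is scored.

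The research question asks for less inappropriate therapy with no increase in UTI or pyelonephritis, and the Implications section hopes to show that untreated infection is rare. A scoring rule that can lose such infections bears directly on that claim.

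**Working it through.** **1. The texts side by side**

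| Question | What the plan says |
|---|---|
| Is a removed patient analysed? | Removed from the study, yet all randomized are analysed |
| Is a removed patient followed to day 7? | Not stated |
| Is adverse event the same as untreated UTI? | Not stated. The Methodology section names untreated UTI as a patient risk, but also uses the term for harm caused by inappropriate treatment, and lists "outcomes (untreated UTI or pyelonephritis") apart from it |
| Is a UTI treated because of a review counted as untreated? | Efficacy: the words about prescribing by physicians suggest yes. Safety: nothing settles it |

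**2. Sample size used below.** The plan's 84 reproduces. With rates 0.45 and 0.15, two-sided 5% and 80% power, the pooled formula gives [1.960√(2·0.30·0.70) + 0.842√(0.45·0.55 + 0.15·0.85)]² / 0.30² = 35.4. The continuity correction, (35.4/4)·[1 + √(1 + 4/(35.4·0.30))]², gives 41.8, so 42 per arm and 84 in all. Recruitment of 100 in two equal groups gives 50 per arm.

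**3. How many patients might be affected?** Let r be the patients in one arm whose UTI is found untreated at a review and then treated. The documents do not give r. The only guide is the pilot study in the Literature Review.

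- If its 2% is of 415 specimens: 0.02 × 415 = 8.3 UTIs, 0.178 × 415 = 73.9 positives, and 8.3/73.9 = 11.2%, or 5.6 of 50. If 25% to 75% were untreated at review (assumed), r is 1.4 to 4.2.
- If the 2% is of positive cultures: 1.0 of 50, and r is 0.25 to 0.75.
- The pilot reported no incidence of UTI or sepsis, so r may be 0.

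This base is weak: the same paragraph mentions 37 positives reported in the restricted way, which is not reconciled with 73.9.

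**4. What the scoring choice does to the safety result.** Restricted minus control, 50 per arm, Newcombe 95% intervals, hypothetical counts:

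| Untreated UTI, restricted v control | Difference (points) | 95% interval |
|---|---|---|
| 0 v 0 (all scored as treated) | 0 | -7.1 to 7.1 |
| 1 v 1 counted | 0 | -8.7 to 8.7 |
| 1 v 0 counted | 2 | -5.3 to 10.5 |
| 0 v 1 counted | -2 | -10.5 to 5.3 |
| 4 v 0 counted | 8 | -0.6 to 18.8 |

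If the four patients in the last row were dropped, the restricted arm would show 0 of 46 (exact interval 0 to 7.7%). Even 4 v 0 is not significant (Fisher two-sided p = 0.117).

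**5. Timing.** Reviews run from collection, but randomization happens when the culture is positive, and patients on antibiotics at collection are excluded. Every patient therefore starts untreated. The documents give no culture turnaround time. If a result arrives near or after 24 hours, counting every UTI untreated at the 24-hour review would record failures in both arms before either report could act.

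**The case against.** The removal sentence stands among the patient-protection statements and can be read as meaning only that restricted reporting stops and the patient is treated. Intention to treat exists for patients who leave their assigned management, so on that reading nothing conflicts. Outcomes come from health records, and no sentence says those records stop being read. This reading is sensible and may be what the sponsor intends, but the plan does not say so. Intention to treat would keep the patient in the denominator without settling how the event is scored.

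Adverse event may mean something else, such as sepsis or a drug reaction. An untreated UTI would then not itself trigger removal. This objection stands against the second gap but not against the first.

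For efficacy, the outcome is worded in terms of what physicians prescribe, which largely answers the scoring question. What stays open is mainly safety.

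A reader might go further and infer that the rule biases the trial toward restricted reporting, because that arm has identification and susceptibility withheld, and that it hides an excess of 10 to 19 points. The documents do not support this. Those upper limits need one to four events in the restricted arm and none in control, while the same reviews apply to both arms, and the restricted report still says the culture is positive and invites a call. The plan sets no safety margin, so no planned decision is shown to change.

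**Conclusion.** The point holds as a conflict in the text and an open scoring rule. Read literally, removal contradicts the analysis of all randomized patients, and may shorten follow-up. If adverse event includes untreated UTI, a primary safety event can be dropped, scored as treated or counted, and each is compatible with the plan.

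A reader might infer that follow-up certainly ends, or that events will certainly be lost. Neither is established: both depend on how an undefined term and the word removed are applied. The size and direction of any bias are unknown. If no such patient occurs, no safety event is miscounted. If they occur equally in both arms, the estimated difference does not move and only its precision does. A one-sided effect, in either direction, needs an imbalance for which the documents give no figure.

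The change is still worth making before recruitment, because the outcome affected is the safety result and the remedy is nearly free.

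**What to change.** In Methodology:

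- Define adverse event.
- Replace removal with this: the full report is released and standard treatment given, and the patient stays in follow-up to day 7 and in the intention-to-treat analysis.

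In Research Objectives:

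- State that a UTI or bacteremia first treated because of a study review counts as untreated for safety, and such a UTI counts as inappropriate therapy for efficacy, in both arms.
- Apply this only once the physician has had a fixed, pre-stated time in which to treat, measured from the report and not from collection.

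On the case report form, record the date of first treatment and what prompted it. Report these patients by arm, with an interval for the difference, and add a sensitivity analysis that scores them as treated.

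**Cost.** A few sentences and two form fields. Day-7 follow-up is already planned, the sample size is unchanged, and patients are treated just as promptly. One downside is that some patients the ward would have treated later are counted as untreated.

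The other is efficacy power, found by enumerating the two-sided t test at 50 per arm. It stays at 92% if the planned 15% already includes these patients. If it does not, and one to four of them (2 to 8 points) fall only in the restricted arm, power is 87%, 81%, 73% or 65%. If the same points are added to both arms, it is 91% to 89%. The loss is therefore small unless such events are several and concentrated in the restricted arm.

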### **Implications**

The implications of significant results will be powerful. A reduction in inappropriate antibiotic treatment may reduce complications of treatment such as diarrhea due to *Clostridium difficile*, selection of bacteria towards drug resistance, and cost of treatment. A demonstration that untreated UTI or pyelonephritis is rare may educate physicians and nurses to be more

selective in urine collection. This could reduce workload and cost in the microbiology laboratory. The results will generalize to adult inpatients in Canada and around the world. If the results agree with the previous study, evidence may justify restriction of access to urine culture based on pretest probability of UTI.

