The use of restricted reporting could provide a cheap and sustainable intervention to reduce inappropriate treatment for AB. Because the study was not randomized, the estimate of true effect may be biased. An ideal design would include randomization of positive cultures between restricted and standard reporting.

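### The Implications section claims worldwide generalization and points towards restricting urine culture by pretest probability; a short two-hospital trial of how positive results are reported supports neither

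*Combined protocol and SAP*

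**What the plan says.** Three statements in the Implications section matter here.

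- Generalization, with no hedge: "The results will generalize to adult inpatients in Canada and around the world".
- Access to culture, hedged by a condition and by the word may: "If the results agree with the previous study, evidence may justify restriction of access to urine culture based on pretest probability of UTI".
- Rarity, also conditional: showing that untreated UTI or pyelonephritis is rare might teach staff to collect urine more selectively, with savings for the laboratory.

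The Methodology section describes the trial that would feed these statements. Entry is by positive culture: "Inclusion criteria will include consecutive positive urine cultures collected from adults in acute care". On sites: "Inpatients must be admitted to Health Sciences Center or St. Clare's Mercy hospitals only". On selection: "Exclusion criteria will include pregnancy, antibiotic treatment at the time of collection, collection from an indwelling urinary catheter, patients in the Intensive Care Unit", and also patients with neutrophils below 1.0 within 7 days. On duration: "This will require approximately ten days of recruitment". A designated person "will review patient charts at 24 and 72 hours and 7 days after collection to ensure patients experience minimal adverse events", and a patient with an adverse event leaves the study and receives usual treatment. The only randomized difference is whether the report gives identification and susceptibility or instead invites a call to the laboratory.

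**The concern.** The Implications section tells readers what the result will mean, and the protocol plans publication. Read as written, a positive trial could be cited for a different policy (not culturing, or culturing only above some pretest probability) and in patients the trial excluded. Not culturing would also take away the protection that restricted-arm physicians have, which is that a full result exists and can be had by telephone.

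The safety statement has a related weakness. Untreated UTI is the patient risk that the protocol itself names. Its frequency would be measured while study staff look at each chart three times, expressly to keep harm low. A hospital that adopted only the new report format would not have those reviews.

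**Working it through.** **1. The plan's own sample size.** Inputs from Methodology: 45% versus 15%, two-sided type 1 error 5%, power 80%, equal groups. The mean proportion is 0.30 and the difference d is 0.30.

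- Uncorrected: n = [1.960·√(2·0.30·0.70) + 0.842·√(0.45·0.55 + 0.15·0.85)]² / 0.30² = (1.270 + 0.515)² / 0.09 ≈ 35.4, that is 36 per arm.
- Continuity-corrected: n' = (n/4)·[1 + √(1 + 4/(n·d))]² with n = 35.4 gives 41.8, that is 42 per arm and **84 in total**, the stated figure.
- Allowance for missing data: 84 / (1 − 0.16) = 100, or 50 per arm.

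The size is therefore reproduced, and it rests on the prescribing outcome alone. Research Objectives and Methodology give no expected rate, margin or power for the safety outcome.

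**2. The ten days.** About 40 positives a day × 25% inpatient = 10 a day, and 100 / 10 = 10 days. This assumes that no one is excluded. At assumed eligibility of 75%, 50% or 25% (not in the documents) it becomes about 13, 20 or 40 days, which is still one short period.

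**3. Claims set against the design.**

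- *Adult inpatients worldwide.* The sample comes from one laboratory and two hospitals. Patients who are pregnant, in intensive care, neutropenic, sampled from an indwelling catheter or already on antibiotics are excluded. The Implications sentence carries none of these limits.
- *Restricting culture by pretest probability.* Every patient in both arms has been cultured and is positive before randomization. No pretest probability is recorded, no culture-negative patient is enrolled and no ordering rule is tested. Agreement with the cited pilot cannot fill the gap. That study also tested restricted reporting, and the Literature Review says its estimate may be biased because it was not randomized.
- *Rarity of untreated UTI.* Chart review at 24 hours, 72 hours and 7 days, with usual treatment after an adverse event, is additional to the reporting policy.

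**4. Precision on rarity, restricted arm of 50.** For zero events the exact two-sided 95% upper limit is 1 − 0.025^(1/50) = **7.1%**. One event gives 0.05% to 10.6%, and two give 0.5% to 13.7%. If the true rate were 2% (an assumption), zero events would be seen with probability 0.98^50 = 36%.

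These figures use all restricted-arm patients as the denominator. A denominator of UTI cases only would be much smaller. As an illustration, suppose that the pilot's 2% with UTI and 17.8% culture-positive share a denominator and that every UTI was culture-positive. Then 2 / 17.8 = 11% of positives, about 6 of 50, would be UTIs, and zero untreated among 6 has an upper limit of 1 − 0.025^(1/6) = 46%.

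**The case against.** The strongest reply is that the Implications section drives nothing. Research Objectives confines the question to inpatients with positive cultures reported by one laboratory, and the hypothesis concerns prescribing. Two of the three statements are conditional. This stands in part: only the generalization sentence is unhedged, and the point is about interpretation, not a flaw in the comparison.

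Second, access to urine culture might mean access to results, since the Literature Review describes the pilot's reporting as a barrier to positive results. That reading is possible. However, the neighbouring sentences, on more selective collection and lower laboratory workload, favour the reading about culturing itself. On either reading no pretest probability is measured.

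Third, treatment after an adverse event does not erase a UTI already recorded as untreated, and the documents do not say that a review without an adverse event leads to release of results. Both are correct. How far the reviews lower the observed rate is therefore unknown, which is a reason to record their consequences.

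A reader might go further in three ways that the documents do not support.

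- *That the trial plans to conclude the intervention is sustainable.* The Literature Review says only: "The use of restricted reporting could provide a cheap and sustainable intervention to reduce inappropriate treatment for AB". This is hedged rationale, and the Implications section does not repeat it.
- *That the generalization gap can be sized from the daily specimen counts.* Those counts include outpatients and negative cultures, while the claim concerns adult inpatients. The share of inpatient positives excluded is not given.
- *That the number of review-triggered actions bounds the hidden untreated UTIs.* It does not. Such a count could include UTIs already recorded as untreated, and actions in patients with asymptomatic bacteriuria, who cannot have an untreated UTI.

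**Conclusion.** The concern holds as a limit on what may be concluded. The worldwide claim is unsupported as written. Restriction of culture by pretest probability is untested here and can only be a hypothesis. Rarity of untreated UTI could be described only for patients under scheduled review, and imprecisely: with 50 restricted-arm patients and no events, rates up to 7.1% remain compatible with the data. That figure assumes full recruitment, equal arms and all restricted-arm patients in the denominator.

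A reader might infer that the section commits the sponsor to all three conclusions, or that the trial itself is unsound. Neither follows. The access and rarity sentences are conditional, and the randomized comparison of inappropriate treatment remains valid for the enrolled setting, with its sample size reproduced. The direction and size of any effect of chart review on the untreated-UTI rate cannot be derived from the documents. The change is worth making before recruitment because the consequences of each review may not be recoverable afterwards.

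**What to change.** 1. In Implications, replace the worldwide sentence with the conclusion the trial can reach: the short-term effect of restricted versus standard reporting on prescribing, in the population defined by the Methodology criteria at the two hospitals, under scheduled chart review.
2. In the same section, label restriction of culture by pretest probability as a hypothesis for a separate study.
3. Add one case report form field, completed at the reviews already planned: did this study review lead to release of results or to treatment? Report the answers by arm, separately for adjudicated UTI and asymptomatic bacteriuria.
4. Report untreated UTI by arm with exact confidence intervals.
5. Add a sensitivity analysis that counts as untreated those adjudicated UTIs treated only after a study review and not already counted.

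The cost is rewording one section, one extra field and one extra table. The downside is a less far-reaching stated conclusion. The primary efficacy analysis, the sample size and patient management do not change.
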